**10.3 SAFETY ANALYSIS**

Not applicable.

**11. QUALITY CONTROL**

Greater details are documented in the NIS-DMRP.

## ANNEX 1. ADDITIONAL INFORMATION

Table 1. Baseline characteristic of the study cohort

	Before propensity score match				After propensity score match			
	Tio/Olo cohort		ICS/LABA cohort		Tio/Olo cohort		ICS/LABA cohort	
	N	%	N	%	ASD	N	%	ASD
Gender								
Male								
Female								
Age								
40~54								
55~69								
70~84								
85+								
Calendar year of cohort entry								
2014								
2015								
2016								
2017								
2018								
2019								
Season of index date								
Spring (Mar-May)								
Summer (Jun-Aug)								
Fall (Sep-Nov)								
Winter (Dec-Feb)								
COPD treatments in 1 year prior to index date								
LAMA								
LABA								
ICS								
ICS+LAMA free combination								
Use of other respiratory drugs in 1 year prior to index date								
Mucolytics								
Theophylline								
Short-acting beta-agonists (SABA)								
Short-acting muscarinic antagonists (SAMA)								

# BOEHRINGER INGELHEIM Group of Companies

## Statistical and Epidemiological Analysis Plan (SEAP) for Non-Interventional Studies (NIS)

c40729787-01

Page 24 of 38

Proprietary confidential information © 2022 Boehringer Ingelheim International GmbH or one or more of its affiliated companies

	Before propensity score match				After propensity score match					
	Tio/Olo cohort		ICS/LABA cohort		ASD	Tio/Olo cohort		ICS/LABA cohort		
	N	%	N	%		N	%	N	%	
Acute COPD exacerbation in 1 year prior to index date										
Moderate exacerbation										
0										
1										
>=2										
Severe exacerbation										
0										
1										
>=2										
All exacerbations (Moderate + Severe)										
0										
1										
>=2										
Acute COPD exacerbation in the 30 days prior to index date										
Moderate exacerbation										
0										
1										
>=2										
Severe exacerbation										
0										
1										
>=2										
All exacerbations (Moderate + Severe)										
0										
1										
>=2										
Hospitalizations caused by exacerbation of COPD in 1 year prior to index date										
0										
1										
>=2										
All-cause hospitalizations in 1 year prior to index date										
0										

Proprietary confidential information © 2022 Boehringer Ingelheim International GmbH or one or more of its affiliated companies

	Before propensity score match				After propensity score match					
	Tio/Olo cohort		ICS/LABA cohort		ASD	Tio/Olo cohort		ICS/LABA cohort		ASD
	N	%	N	%		N	%	N	%	
1										
>=2										

**Comorbidities:**

Cardiovascular disease  
 Cerebrovascular disease  
 Diabetes  
 Chronic kidney disease  
 Pneumonia  
 Cancer  
 Cirrhosis

**Charlson Comorbidity Index  
(CCI)**

History of medications dispensed in 1 year prior to index date

Cardiovascular drugs:  
 Antihypertensives  
 Antiarrhythmics  
 Nitrates  
 Heart failure medications  
 Lipid-lowering medications  
 Blood glucose-lowering medications  
 Anticoagulants and antiplatelet agents  
 Antibiotics  
 Antineoplastic agents

**COPD severity**

Mild  
 Moderate  
 Severe  
 Very severe

Proprietary confidential information © 2022 Boehringer Ingelheim International GmbH or one or more of its affiliated companies

**Table 2. Hazard ratios for COPD exacerbation, Tio/Olo users vs. ICS/LABA users**

After PS match	Moderate exacerbation	Severe exacerbation	All exacerbation (Moderate + Severe)
	HR (95% CI)	HR (95% CI)	HR (95% CI)
Tio/Olo			
ICS/LABA	Reference	Reference	Reference
	Adjusted* HR (95% CI)	Adjusted* HR (95% CI)	Adjusted* HR (95% CI)
Tio/Olo			
ICS/LABA	Reference	Reference	Reference

\* If needed, list of adjusted covariates will be listed.

**Table 3. Hazard ratio for time to first triple therapy escalation, Tio/Olo users vs. ICS/LABA users**

After PS match	Triple therapy escalation	
	HR (95% CI)	Adjusted* HR (95% CI)
Tio/Olo		
ICS/LABA	Reference	Reference

\* If needed, list of adjusted covariates will be listed.

**Table 4. Incidence rates of triple therapy initiation among the two cohorts, incidence rate ratio and incidence difference estimates**

After PS match	No. with events	Person-years	Incidence Rate (95% CI)	IRR (95% CI)	Adjusted* IRR (95% CI)	Incidence difference (95% CI)
Triple therapy escalation						
Tio/Olo						
ICS/LABA						
	Reference	Reference	Reference			

\* If needed, list of adjusted covariates will be listed.

**Table 5. Hazard ratio for time to first hospitalization for community-acquired pneumonia, Tio/Olo users vs. ICS/LABA users**

After PS match	Hospitalization for community-acquired pneumonia	
	HR (95% CI)	Adjusted* HR (95% CI)
Tio/Olo		
ICS/LABA	Reference	Reference

\* If needed, list of adjusted covariates will be listed.

Table 6. Annualized rates of prescription of rescue medications and moderate or severe COPD exacerbations

After PS match	No. of patients with events	No. of events	Person-years	Annualized rate (95CI)	Annualized rate ratio (95CI)	Adjusted* rate ratio (95CI)
Rescue medication						
Tio/Olo						
ICS/LABA						
Reference Reference						
Moderate exacerbation						
Tio/Olo						
ICS/LABA						
Reference Reference						
Severe exacerbation						
Tio/Olo						
ICS/LABA						
Reference Reference						
All exacerbation (Moderate + Severe)						
Tio/Olo						
ICS/LABA						
Reference Reference						

\* If needed, list of adjusted covariates will be listed.

## Appendix 1. SAS code template for negative binomial model in the analysis of the secondary outcomes of interest

The following codes are provided by Boehringer Ingelheim statistician

```
PROC GENMOD DATA=test;
CLASS treat (ref='LABA/ICS') cova_cat;
MODEL ep_count = treat cova_cat cova_con /
DIST=negbin LINK=LOGTYPE3 OFFSET=logt;
LSMEANS treat / DIFF CL;
ESTIMATE 'Treatment effect on ratio-scale' treat 1 -1 / EXP;
RUN;
```

(In the model,  
treat: Tio+Olo group OR LABA/ICS group;  
Cova\_cat: categorical covariates;  
Cova\_con: continuous covariates)

For univariate analysis, Cova\_cat and Cova\_con are not applicable.

For calculating incidence rate ratio with 95% CI of triple therapy initiation (Tio+Olo vs. LABA/ICS),  
ep\_count (response): 1 (triple therapy initiation occurred per patient) or 0 (triple therapy initiation not occurred per patient);  
logt: nature log of the time at risk (first event per patient)

For calculating ratio (with 95% CI) of annualized rate of moderate or severe COPD exacerbations and annualized rate of prescriptions of rescue medications (Tio+Olo vs. LABA/ICS),  
ep\_count (response): number of events per patient  
logt: nature log of the time at risk per patient

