### **(4). Annualized rate of prescriptions of rescue medications after the index date**

Rescue medications are defined as free or combination use of SABA or SAMA. Detailed drug ATC codes are listed in Annex.

For annualized rates, it will be calculated for each cohort as follows:

Annualized rate among the Tio+Olo cohort = (total number of events in the Tio+Olo cohort during the given time period) / (total person-year at risk from current use of Tio+Olo during the given period)

Annualized rate among the comparison cohort = (total number of events in the comparator LABA/ICS cohort during the given time period) / (total person-year at risk from current use of comparator LABA/ICS during the given period)

For annualized rate and total number of prescriptions of rescue medications, the rate ratio of Tio+Olo – exposed group relative to LABA/ICS group, along with 95% CI will be derived using univariate negative binomial model.

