## **10. DATA ANALYSIS**

### **10.1 MAIN ANALYSIS**

All variables, including patient characteristics, baseline measures, and outcomes, will be analyzed descriptively.

- For all analyses, variables will be reported as follows: Continuous variables (e.g., age) will be presented as means (with standard deviation, SD) and/or medians (with interquartile range, IQR), minimum, maximum.

- Categorical variables (e.g., sex) will be presented as absolute and relative frequencies.

All analyses will be presented for each treatment group (Tio+Olo vs LABA/ICS) overall. We will first describe formation of the study cohort. Propensity score (PS) matching will be used to generate two comparable treatment groups. All covariates, except season of index date, will be used to estimate the propensity score with logistic regression. Patients in LABA/ICS group will be individually matched to patients in the Tio/Olo group with 1:1 ratio. A caliper of 0.06 standard deviation of logit (propensity score) will be used to define the range of estimated PS within which to select the comparator. Within that range the LABA/ICS patient with the closest estimated propensity score to the Tio/Olo patient will be selected.

Patient characteristics at baseline in patients treated with Tio+Olo and patients treated with LABA/ICS will be described separately using standard descriptive statistics after propensity score matching. Absolute standardized differences (ASDs) will be used to compare the characteristics between the two groups after propensity score matching, in which a  $>0.1$  ASD indicates a meaningful difference.

All the analyses for primary outcome and secondary outcomes will be performed on patients after propensity score matching. Baseline characteristic table shell are provided in [Table 1](#). The propensity score matching will be carried out once without re-matching.

For the analysis of the primary outcome, individuals will be followed up from the index date until the first moderate or severe COPD exacerbation. The data after the earliest date of the following event would be censored:

- 1) disenrollment
- 2) the end of the study period
- 3) death
- 4) discontinuation of index drug use (a lapse of 45 days without subsequent prescription)
- 5) switching from Tio/Olo to ICS/LABA or from ICS/LABA to Tio/Olo
- 6) escalation to triple therapies (ICS/LAMA/LABA free or fix dose combination)

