The analysis of the secondary objectives related to annualized rate of prescriptions of rescue medications, the rate ratio of Tio+Olo – exposed group relative to LABA/ICS group, along with 95% CIs will be derived using univariate negative binomial model. Individuals in the study cohort will be followed from the index date until the earliest of the date of:

- 1) disenrollment;
- 2) the end of the study period;
- 3) death;
- 4) discontinuation of the index drug use (a lapse of 45 days without subsequent prescription);
- 5) switching from Tio/Olo to ICS/LABA or from ICS/LABA to Tio/Olo

In the event that there are baseline covariates with unequal distribution between the treatment groups, defined as absolute standardized difference larger than 0.1, the covariate(s) will be included in a multiple regression model in addition to the exposure status (Tio/Olo or LABA/ICS).

For incidence rates, it will be calculated for each cohort as follows:

Incidence rate among the Tio+Olo cohort = (total number of patients in the Tio+Olo cohort experiencing an event of interest for the first time during the given time period) / (total person-time at risk from current use of Tio+Olo during the given period)

Incidence rate among the comparison cohort = (total number of patients in the comparator LABA/ICS cohort experiencing an event of interest for the first time during the given time period) / (total person-time at risk from current use of comparator LABA/ICS during the given period)

The incidence rate ratio (IRR) and incidence difference for the outcome in the Tio+Olo - exposed group relative to that in the comparator group will be derived as follows:

Incidence rate ratio = incidence rate from the Tio+Olo cohort divided by the incidence rate from the matched comparator cohort.

Incidence difference = incidence rate from the Tio+Olo cohort – incidence rate from the matched comparator cohort

For annualized rates, it will be calculated for each cohort as follows:

Annualized rate among the Tio+Olo cohort = (total number of events in the Tio+Olo cohort during the given time period) / (total person-year at risk from current use of Tio+Olo during the given period)

Annualized rate among the comparison cohort = (total number of events in the comparator LABA/ICS cohort during the given time period) / (total person-year at risk from current use of comparator LABA/ICS during the given period)

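### The confidence intervals for the rescue-prescription and exacerbation rate ratios rest on an unchecked negative binomial variance and may be too narrow or too wide; use empirical standard errors.

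*SAP*

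**What the plan says.** SAP 7.2.2 (4) says "Rescue medications are defined as free or combination use of SABA or SAMA". It compares the arms by a ratio of annualized rates, "along with 95% CI will be derived using univariate negative binomial model". SAP 10.1 repeats this for rescue prescriptions ("with 95% CIs will be derived using univariate negative binomial model. Individuals in the study cohort") and uses a negative binomial model for the annualized exacerbation rate too. Both sets of ratios go into SAP Table 6.

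SAP Appendix 1 gives the code: PROC GENMOD with "DIST=negbin LINK=LOGTYPE3 OFFSET=logt" (read here as a log link and a TYPE3 option run together when the PDF was read). The response is the "number of events per patient" and the offset is the "nature log of the time at risk per patient". The ratio comes from "ESTIMATE 'Treatment effect on ratio-scale' treat 1 -1 / EXP". The template has no REPEATED statement, and nothing visible in either document plans an empirical variance, a bootstrap or a check of the count distribution. Covariates enter only if an absolute standardized difference exceeds 0.1, which addresses imbalance and not the form of the variance.

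**The concern.** The stated comparison is between mean rates. The model-based standard error carries an extra condition: the variance of each patient's count must follow the negative binomial form, with one dispersion for everyone. The maximum-likelihood dispersion is driven largely by the many zeros and low counts. If the upper tail is heavier than that fit implies, the variance is understated. If most patients are complete non-users and the rest are fairly regular users, the fit to the zeros overstates it.

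Prescription counts could plausibly depart in either direction. A Table 6 interval could then present a chance imbalance in a few heavy users as a drug difference, or be so wide that it hides a real one. Nothing visible in the plan would reveal which had happened.

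**Working it through.** **Plan's own figure.** The documents give no rate, dispersion, error rate or power for these outcomes, so there is nothing to reproduce. The 4,978 patients in protocol 9.5 are for the primary time-to-event outcome; only the arm size of 2,489 is borrowed.

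**Inputs from the documents.** Negative binomial, log link, log-time offset, model-based standard error (SAP Appendix 1); 1:1 arms (SAP 10.1: "will be individually matched to patients in the Tio/Olo group with 1:1 ratio"); 95% interval.

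**Assumed inputs.** The distribution of patient rates, and follow-up of either 1 year for all or exponential with mean 0.5 year (30 days to 6 years).

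**Closed form, 1-year follow-up.** With mean m, dispersion k and n per arm, SE(log ratio) = √[2(1/m + k)/n]. The template puts in the fitted k. The true value uses k = Var(rate)/m². The chance that the 95% CI excludes 1 under equal rates is about 2[1 − Φ(1.96 × model SE / true SE)].

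- *Gamma, m = 1, k = 4.* Fitted k is 3.99. SE = √(2 × 5/2489) = 0.063, in agreement with the true value, so about 5%.
- *Lognormal, SD 1.5, m = 1.* True k = exp(2.25) − 1 = 8.49, true SE = √(2 × 9.49/2489) = 0.087. Fitted k is 3.23, model SE = √(2 × 4.23/2489) = 0.058. About 19%.
- *5% of patients at 12 per year, the rest at 0.5.* m = 1.075, true k = (7.4375 − 1.1556)/1.1556 = 5.44, true SE 0.072. Fitted k is 2.83, model SE 0.055. About 13%.
- *10% at 10 per year, the rest never.* m = 1, true k = 9, true SE 0.090. Fitted k is 32.4, model SE 0.164. Below 0.1%.

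**Simulation.** Equal rates, mean about 1 per year, 2,000 replicates per cell (Monte Carlo SE √(0.05 × 0.95/2000) = 0.5 points). Entries are the percentage of intervals excluding 1, for 1-year / exponential follow-up.

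| Patient rates | Use held by top 10% | Template SE | Sandwich SE |
|---|---|---|---|
| Gamma, k = 4 | 59% | 4.3 / 4.4 | 4.3 / 4.7 |
| Gamma, k = 10 | 81% | 5.4 / 5.4 | 5.6 / 5.2 |
| Lognormal SD 1.0 | 39% | 8.0 / 7.5 | 5.3 / 5.6 |
| Lognormal SD 1.5 | 59% | 16.8 / 15.4 | 5.1 / 4.5 |
| Lognormal SD 1.5, capped at 24/yr | 57% | 10.3 / 8.5 | 5.1 / 5.1 |
| 2% at 20/yr, rest 0.5/yr | 50% | 24.4 / 17.9 | 5.7 / 5.4 |
| 5% at 12/yr, rest 0.5/yr | 58% | 13.5 / 9.7 | 5.7 / 4.9 |
| 10% at 8/yr, rest 0.3/yr | 74% | 5.7 / 5.3 | 5.5 / 5.3 |
| 10% at 10/yr, rest 0.1/yr | 91% | 1.3 / 1.5 | 5.0 / 4.9 |
| 30% gamma users, mean 3.3/yr, rest never | 70% | 1.7 / 3.3 | 4.8 / 5.5 |
| 10% at 10/yr, rest never | 99% | 0.1 / 0.4 | 4.7 / 4.8 |

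Over all 18 rate shapes and both follow-up patterns (36 combinations), the template ranged from 0.1% to 35.9%, the top being an uncapped lognormal with SD 2. The sandwich ranged from 4.2% to 6.1%.

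**Other rates.** With a mean of 3 per year, median follow-up of about 7 months and 500 replicates, lognormal SD 1.0 / 1.25 / 1.5 gave 8.0 / 13.4 / 20.6% with the template and 3.8 / 3.6 / 6.2% with the sandwich. Four shapes with 50 to 70% never-users gave 0.0 to 2.8% with the template. For exacerbations, 25% by 103 days (protocol 9.5) implies −ln(0.75)/103 × 365.25 = 1.02 per year. At a mean of 1 per year the same three SDs gave 8.6 / 10.2 / 15.0% with the template and 3.8 to 5.6% with the sandwich.

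**The case against.** A reader might infer that because rescue use is probably concentrated in a few patients, the planned interval must be too narrow by a known factor, with error two to four times 5%. The documents do not support that. Concentration alone is harmless: gamma rates with 81% of use in the top tenth stay near 5%. A population of many non-users with a minority of regular users, which is easy to imagine here, can make the interval too wide. The largest inflation also needs extreme patients. An uncapped lognormal with SD 1.5 and mean 3 per year puts its 99.9th percentile at exp(ln 3 − 1.125 + 3.09 × 1.5) ≈ 100 prescriptions a year. Capping rates at 24 per year, itself an assumption, brings the error down to about 6 to 10%.

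Strictly, the model does not even need gamma rates; it needs its variance function to be right. The outcomes are secondary and the visible text plans no formal test of them. A subsection between SAP 10.1 and 10.3 is redacted and may hold sensitivity analyses.

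All of this stands, and it removes any claim about direction or a fixed multiple. It does not show that the planned interval is right. A sensitivity analysis, if one exists, would leave the main template as it is.

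**Conclusion.** The point holds as a weakness of method. The Table 6 rate-ratio intervals depend on a variance assumption that the visible plan does not check. Under equal rates they exclude 1 about 5% of the time if rates are gamma. The figure is about 8 to 20% with lognormal rates of SD 1.0 to 1.5 or a small heavy-use group over occasional users (single scenarios up to 24%), nearer 6 to 10% if the SD 1.5 rates are capped at 24 per year, and about 0 to 3% when most patients never use rescue medication. All of these rest on assumed rate distributions and follow-up, and the documents cannot place the study among them.

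The consequence is a misstated 95% CI for two secondary outcomes. Reading this as a failed hypothesis test, or as a problem for the primary Cox analysis or the sample size, would go beyond the documents. The change is worth making because it corrects the interval in either direction.

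**What to change.** For the two count outcomes, add a patient identifier to the CLASS statement in SAP Appendix 1 and the line `REPEATED SUBJECT=patient / TYPE=IND;`. State in SAP 10.1 that the rate-ratio CIs in Table 6, unadjusted and adjusted, use empirical (sandwich) standard errors. The programmer should confirm that the ESTIMATE output reports them.

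The cost is one SAS line, one CLASS variable and one sentence. The point-estimate model is unchanged. Under gamma rates nothing material is lost: in a check at the same arm size the mean standard error was 0.0463 either way. The downside is that intervals will be wider than the current template gives if the tail is heavier than gamma.

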## Appendix 2. ICD-9/10-CM codes and procedure codes for identification of study cohorts

	ICD9	ICD10
For inclusion criteria		
COPD	491.x, 492.x, 496	J41.x, J42, J43.x, J44.x
For exclusion criteria		
Asthma	493.x	J45.x
Allergic rhinitis	477.x	J30.x
Lung cancer	162.x	C33.x, C34.x, C7A.090, D02.2
Interstitial lung disease	238.1, 500, 501, 502, 503, 504, 505, 506.4, 508.1, 508.8, 515, 516.x	J60, J61, J62.x, J63.x, J64, J65, J66.x, J68.4, J70.x (no 70.2), J84.1x (no J84.114), J84.2, J84.3, J84.89, J84.9, J94.1

Procedure codes	Content
68037A	Lung transplantation
68037B	Lung transplantation - Unilateral lung
68047B	Lung transplantation - bilateral sequential or en bloc double lung

## Appendix 3. COPD medications

Groups	Drug name	ATC code
LAMA	Tiotropium bromide	R03BB04
	Glycopyrrolate	R03BB06
	Umeclidinium	R03BB07
LABA	Salmeterol	R03AC12
	Formoterol	R03AC13
	Procaterol	R03AC16
	Indacaterol	R03AC18
	Olodaterol	R03AC19
ICS	Beclometasone(=beclomethasone)	R03BA01
	Budesonide	R03BA02
	Fluticasone	R03BA05
	Ciclesonide	R03BA08
ICS/LABA	Salmeterol and Fluticasone	R03AK06
	Formoterol and Budesonide	R03AK07
	Formoterol and Beclometasone	R03AK08
	Vilanterol and Fluticasone furoate	R03AK10
	Formoterol and Fluticasone	R03AK11
LABA/LAMA	Vilanterol and Umeclidinium bromide	R03AL03
	Indacaterol and Glycopyrronium bromide	R03AL04
	Olodaterol and Tiotropium bromide	R03AL06
LABA/LAMA/ICS	Vilanterol, Umeclidinium bromide and Fluticasone furoate	R03AL08
	Formoterol, Glycopyrronium bromide and Beclometasone	R03AL09

Proprietary confidential information © 2022 Boehringer Ingelheim International GmbH or one or more of its affiliated companies

## Appendix 4. ICD codes and operational definition of comorbidities

	Comorbidities:	ICD codes	Operational definition
1.	Diabetes	ICD9: 250 ICD10: E10.x-E11.x	Either inpatient diagnosis or more than twice outpatient diagnosis
2.	Cardiovascular disease	ICD9: 250.7, 401-405, 410-414, 425-428, 429.1-429.3, 441, 442, 458 ICD10: E10.5x, E11.5x, I10-I13.x, I15.x, I20.x-I22.x, I24.x, I25.x, I42.x-I44, I45.xx, I46.x-I49.x, I50.xx, I51.5, I51.7, I51.9, I71.xx, I79.0, I72.x, I77.7x, I95.x	Either inpatient diagnosis or more than twice outpatient diagnosis
3.	Cerebrovascular disease	ICD9: 430-438 ICD10: I60.x-I63.x, I65.x, I66.x, G45.x, G46.x, I67.x-I69.x	Either inpatient diagnosis or more than twice outpatient diagnosis
4.	Cancer	ICD9: 140-199, 200-208 ICD10: C00-C26, C30-34, C37-39, C40-41, C43-49, C4A, C50-58, C60-69, C70-79, C7A, C7B, C80-86, C88, C90-96,	Inpatient diagnosis.
5.	Chronic kidney disease	ICD9: 585-587, ICD10: N18-19, N26.1, N26.9	Either inpatient diagnosis or more than twice outpatient diagnosis
6.	Pneumonia	ICD9: 480-486, 487.0 ICD10: J10.0, J11.0, J12-J18,	Inpatient diagnosis
7.	Cirrhosis	ICD9: 571.2, 571.5, 571.6 ICD10: K70.3x, K74.3, K74.4, K74.5, K74.6x	Either inpatient diagnosis or more than twice outpatient diagnosis

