### 7.3 COVARIATES

Demographic characteristics and cohort entry information:

- Sex
- Age
- Calendar year of cohort entry
- Season of index date (winter, Dec-Feb; spring, Mar-May; summer, Jun-Aug; fall, Sep-Nov )

Additional characteristics will be defined during the 1-year pre-index baseline period:

- Previous COPD treatments
  - LAMA monotherapy
  - LABA monotherapy
  - ICS monotherapy
  - LAMA/ICS free combination therapy
- Use of other respiratory drugs
  - Mucolytics
  - Theophylline
  - Short-acting beta-agonists
  - Short-acting muscarinic antagonists
- Previous acute COPD exacerbation (measured both 12 months and in the 30 days prior to cohort entry), categorized as 0, 1, or 2+.
  - All exacerbations (Moderate+Severe)
  - An outpatient visit with a diagnosis code for COPD in any field + a prescription for an oral corticosteroid or an antibiotic for respiratory infections (Moderate); prescriptions within 30 days of each other were considered as continuation of the initial exacerbation.
  - Hospitalizations or emergency room visits with a primary diagnosis for COPD

(Severe); hospitalizations or emergency room visits within 30 days of each other were considered as continuation of the initial exacerbation.

- Hospitalizations caused by exacerbation of heart failure in 12 months prior to index date, categorized as
  - 0;
  - 1;
  - 2+.
- All-cause hospitalizations in 12 months prior to index date;
  - 0;
  - 1;
  - 2+.
- Comorbidities:
  - Cardiovascular disease
  - Cerebrovascular disease
  - Diabetes
  - Chronic kidney disease
  - Pneumonia
  - Cancer
  - Cirrhosis
- Charlson Comorbidity Index (CCI)
- History of medications dispensed in the 12 months before or on the index date will be identified from the pharmacy dispensing history:
  - Cardiovascular drugs:
    - antihypertensives;
    - antiarrhythmics;
    - nitrates;
    - heart failure medications
  - Lipid-lowering medications
  - Blood glucose-lowering medications
  - Anticoagulants and antiplatelet agents
  - Antibiotics
  - Antineoplastic agents
- COPD severity

The definition of the severity of COPD in this study was developed based on the information in previous studies, GOLD recommendations and clinical practice in Taiwan, see below. Patients who fulfil criteria for more than one category will be classified as being in the most severe category.

Operational definition of COPD severity:

- Mild:

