## Appendix 5. Drugs of interest

Groups	ATC code
Use of other respiratory drugs	
Mucolytics	R05CB, R05CB01, R05CB02, R05CB03, R05CB04, R05CB05, R05CB06, R05CB10, R05CB11, R05CB91, R05CB92
Theophylline	R03DA04, R03DA54, R03DA74, R03DB04
SABA	R03AC02, R03AC03, R03AC04, R03AC06
SAMA	R03BB01
SABA/SAMA	R03AL01, R03AL02
Drugs for COPD exacerbation treatment	
Oral corticosteroid	H02AB01, H02AB02, H02AB04, H02AB05, H02AB06, H02AB08, H02AB10, H02BX, H02BX91
Antibiotic for COPD exacerbation	J01AA02, J01CA04, J01CR02, J01CR05, J01EE01, J01DC01, J01DC02, J01DC03, J01DC04, J01DC05, J01DC06, J01DC07, J01DC09, J01DC14, J01DD01, J01DD02, J01DD04, J01DD05, J01DD06, J01DD07, J01DD08, J01DD12, J01DD13, J01DD14, J01DD52, J01DD62, J01DE01, J01DE02, J01FA01, J01EA02, J01EA03, J01EA06, J01EA07, J01EA08, J01FA09, J01FA10, J01FA15, J01FA91, J01MA01, J01MA02, J01MA03, J01MA04, J01MA06, J01MA07, J01MA09, J01MA12, J01MA14, J01MA15
Drugs for Medication history	

 
● Cardiovascular drugs
 
	
Anti-hypertensives	C02AA01, C02AA02, C02AA04, C02AB01, C02AB02, C02AC01, C02CA01, C02CA04, C02CA, C02CC02, C02DA01, C02DB02, C02DC01, C02DD01, C02LA01, C02LA50, C02LA51, C02LB01, C02LG02, C02N, C03AA01, C03AA03, C03AA06, C03AA07, C03AA, C03BA04, C03BA08, C03BA11, C03CA01, C03CA02, C03CA04, C03CC01, C03DA01, C03DA04, C03DB01, C03DB02, C03EA01, C03EA, C07AA01, C07AA02, C07AA03, C07AA05, C07AA06, C07AA07, C07AA12, C07AA15, C07AA19, C07AB02, C07AB03, C07AB04, C07AB05, C07AB07, C07AB09, C07AB12,

	C07AG01, C07AG02, C07BA68, C07BB02, C07CA03, C07CB03, C07DA06, C08CA01, C08CA02, C08CA03, C08CA04, C08CA05, C08CA07, C08CA08, C08CA09, C08CA12, C08CA13, C08CA15, C08DA01, C08DB01, C09AA01, C09AA02, C09AA03, C09AA04, C09AA05, C09AA06, C09AA07, C09AA08, C09AA09, C09AA16, C09BA01, C09BA02, C09BA04, C09BB04, C09BB05, C09BB, C09BB, C09CA01, C09CA02, C09CA03, C09CA04, C09CA06, C09CA07, C09CA08, C09CA09, C09DA01, C09DA03, C09DA04, C09DA06, C09DA07, C09DA08, C09DA09, C09DB01, C09DB02, C09DB04, C09DB07, C09DX01, C09DX03, C09DX04, C09XA02, C09XA52, C09XA53, C09XA54
Antiarrhythmics	C01AA04, C01AA05, C01AA07, C01AA08, C01AB01, C01AC01, C01BA01, C01BA02, C01BA03, C01BA04, C01BA08, C01BB01, C01BB02, C01BC03, C01BC04, C01BD01, C01BD07, C01CA02, C01CA04, C01CA06, C01EB10, C01EB17, C07AA01, C07AA02, C07AA03, C07AA05, C07AA07, C07AA12, C07AA15, C07AA19, C07AB02, C07AB03, C07AB04, C07AB05, C07AB07, C07AB09, C07AB12, C08DA01, C08DB01

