Heart failure medications	C01AA04, C01AA05, C01AA07, C01AA08, C01AB01, C01AC01, C01CA02, C01CA07, C01CE02, C01EB09, C01EB17, C03CA02, C03CA04, C03DA04, C07AG02, C09AA01, C09AA02, C09AA03, C09AA04, C09AA05, C09AA06, C09AA07, C09AA08, C09AA09, C09AA16, C09CA01, C09CA02, C09CA03, C09CA04, C09CA06, C09CA07, C09CA08, C09CA09
Nitrates	C01DA02, C01DA05, C01DA08, C01DA14
● Lipid-lowering medications	
Lipid Modifying Agents, Plain	C10AA01, C10AA02, C10AA03, C10AA04, C10AA05, C10AA07, C10AA08, C10AB01, C10AB02, C10AB03, C10AB04, C10AB05, C10AB06, C10AB09, C10AC01, C10AC02, C10AC03, C10AD01, C10AD02, C10AD03, C10AD06, C10AD, C10AX02, C10AX09, C10AX13, C10AX14, C10AX

Proprietary confidential information © 2022 Boehringer Ingelheim International GmbH or one or more of its affiliated companies

Lipid Modifying Agents, Combinations	C10BA01, C10BA02, C10BA03, C10BA05, C10BX03
● Blood glucose-lowering medications	
Insulins and analogues	A10AB01, A10AB03, A10AB04, A10AB05, A10AB06, A10AB30, A10AC01, A10AC03, A10AC30, A10AD01, A10AD03, A10AD04, A10AD05, A10AD06, A10AE01, A10AE04, A10AE05, A10AE06, A10AE54
Blood glucose lowering drugs, excl. insulins	A10BA02, A10BA03, A10BB01, A10BB02, A10BB03, A10BB04, A10BB05, A10BB07, A10BB08, A10BB09, A10BB12, A10BB31, A10BD02, A10BD03, A10BD05, A10BD07, A10BD08, A10BD09, A10BD10, A10BD11, A10BD13, A10BD14, A10BD, A10BD15, A10BD19, A10BD20, A10BD21, A10BD24, A10BF01, A10BF02, A10BG02, A10BG03, A10BH01, A10BH02, A10BH03, A10BH04, A10BH05, A10BJ01, A10BJ02, A10BJ03, A10BJ05, A10BJ06, A10BK01, A10BK02, A10BK03, A10BK04, A10BX01, A10BX02, A10BX03, A10BX08
● Anticoagulants and antiplatelet agents	
Vitamin K antagonists	B01AA02, B01AA03
Heparin group	B01AB01, B01AB04, B01AB05, B01AB06, B01AB10
Platelet aggregation inhibitors excl. heparin	B01AC04, B01AC05, B01AC06, B01AC07, B01AC09, B01AC11, B01AC13, B01AC16, B01AC17, B01AC21, B01AC22, B01AC23, B01AC24, B01AC27, B01AC30
Enzymes	B01AD01, B01AD02, B01AD04, B01AD10, B01AD11
Direct thrombin inhibitors	B01AE07
Direct factor Xa inhibitors	B01AF01, B01AF02, B01AF03
Other antithrombotic agents	B01AX05
● Antibiotic	

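### Heart failure is not isolated as a diagnosis in the propensity score, and Table 1 does not show its balance

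*SAP*

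**What the plan says.** **Diagnosis covariate.** SAP Appendix 4, row 2, is a single flag for cardiovascular disease. Its ICD-9 codes are "250.7, 401-405, 410-414, 425-428, 429.1-429.3, 441, 442, 458". Its ICD-10 codes include "I10-I13.x, I15.x, I20.x-I22.x, I24.x, I25.x, I42.x-I44, I45.xx, I46.x-I49.x, I50.xx". SAP Table 1 gives it one comorbidity line, "Cardiovascular disease". No comorbidity row in Appendix 4 or Table 1 is for heart failure alone.

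**Drug covariate.** Appendix 5 has a separate list of heart failure medications, which contains the run "C03CA02, C03CA04, C03DA04, C07AG02, C09AA01, C09AA02, C09AA03". The antihypertensive list in the same appendix contains "C03BA11, C03CA01, C03CA02, C03CA04, C03CC01, C03DA01, C03DA04" and also "C09AA01, C09AA02, C09AA03, C09AA04, C09AA05, C09AA06, C09AA07, C09AA08, C09AA09, C09AA16". Table 1 has a row for the heart failure drug flag.

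**Admission covariate.** SAP 7.3 lists "Hospitalizations caused by exacerbation of heart failure in 12 months prior to index date, categorized as" 0, 1 or 2+. In the corresponding place, protocol 9.3.3 and SAP Table 1 have admissions for exacerbation of COPD.

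**Use of the covariates.** SAP 10.1 puts every covariate except season into the logistic model for the propensity score, matches once 1:1 with a caliper of 0.06 SD of the logit, and then fits a univariate Cox model. A baseline covariate enters the outcome model only if its absolute standardized difference (ASD) after matching exceeds 0.1.

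**The concern.** Because the outcome model is univariate by default, control of confounding rests on how the matching covariates are defined. A pooled flag can be balanced while its components are not: one arm may hold more hypertension and the other more heart failure, with the same total. If heart failure is related both to the choice between Tio/Olo and ICS/LABA and to the risk of exacerbation or pneumonia admission, an imbalance inside the flag would carry into the hazard ratios. A diagnosis that is not a covariate also cannot trigger the ASD adjustment, and a reader of Table 1 could not see the imbalance.

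**Working it through.** The plan gives no figure for this point, so there is nothing to reproduce. The check has three parts.

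**1. What the diagnosis flag pools** (ICD block meanings applied to the Appendix 4 codes)

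| Group | ICD-9 | ICD-10 |
|---|---|---|
| Hypertension | 401-405 | I10-I13, I15 |
| Ischaemic disease | 410-414 | I20-I22, I24, I25 |
| Cardiomyopathy, heart failure | 425, 428 | I42, I43, I50 |
| Conduction, rhythm | 426, 427 | I44-I49 |

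All of these, with some smaller groups, set the same flag.

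**2. How specific the drug flag is** (set comparison of the Appendix 5 lists)

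- Heart failure list: 33 distinct codes.
- Also on the antihypertensive list: C03CA02, C03CA04, C03DA04, C07AG02, 10 C09AA codes and 8 C09CA codes. That is 4 + 10 + 8 = 22, and 22/33 = 67%.
- Of the other 33 − 22 = 11, on the antiarrhythmic list: 8.
- On neither list: 11 − 8 = 3 (C01CA07, C01CE02, C01EB09).
- C03CA01, C03DA01 and C09DX04 are on the antihypertensive list but not on the heart failure list. For the first two, codes with the same ATC prefix (C03CA, C03DA) are included.

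A single dispensing of any C09AA or C09CA code on the list therefore sets both the antihypertensive and the heart failure flag.

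**3. Illustrative size** (assumed inputs, no drug effect)

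- Hazard without heart failure, from the protocol 9.5 assumption of 25% with an event at 103 days: λ = −ln(0.75)/(103/365.25) = 1.02 per year.
- Assumed: heart failure prevalence after matching p₁ (Tio/Olo) and p₀ (ICS/LABA); event hazard ratio h for heart failure of 1.5 or 2.0; exponential censoring with median on-treatment time of 0.5 or 1 year; 6-year horizon.
- ASD = |p₁ − p₀| / √{[p₁(1−p₁) + p₀(1−p₀)]/2}.
- Survival in arm k: S_k(t) = (1−p_k)e^(−λt) + p_k e^(−λht), with f_k = −S_k′. The Cox limit β solves ∫G(t){f₁ − (f₁+f₀)·S₁e^β/(S₁e^β+S₀)}dt = 0, where G is the censoring survivor function.

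| p₁ vs p₀ | ASD | HR, h = 1.5 | HR, h = 2.0 |
|---|---|---|---|
| 8% vs 12% | 0.04/√0.0896 = 0.13 | 0.984 to 0.985 | 0.973 to 0.975 |
| 9% vs 15% | 0.06/√0.1047 = 0.19 | 0.976 to 0.977 | 0.960 to 0.963 |
| 9% vs 11% | 0.02/√0.0899 = 0.07 | 0.992 | 0.986 to 0.988 |

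The range within each cell is over the two censoring assumptions. Swapping the arms in the first two rows gives HRs of about 1.016 to 1.042. Against the planned HR of 0.90 (log −0.105), the shifts in the first two rows (log −0.015 to −0.041) are 14% to 39% of the planned log effect.

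**The case against.** The strongest objection is that a heart-failure-specific term is already in the score. SAP 7.3 lists heart failure admissions, and SAP 10.1 enters all covariates except season. A reader might infer from Appendices 4 and 5 that the score does not isolate heart failure at all; the SAP as written does not support that. What remains is narrower. The item captures only admitted cases in one year, so heart failure managed as an outpatient is not separately matched. It has no codes in Appendix 4 and no Table 1 row. The protocol and Table 1 name COPD in its place, and the documents do not settle which was meant.

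A reader might also infer that the ASD rule cannot act because Table 1 lacks a row. That is too strong: SAP 10.1 applies the rule to baseline covariates, not to table rows, so the admission item falls under it if it is intended. The rule cannot act on a heart failure diagnosis, because no such covariate exists.

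Third, the score also contains several cardiovascular drug flags, anticoagulants and antiplatelets, chronic kidney disease, diabetes, the Charlson index and all-cause admissions. Matching on these correlates could shrink a heart failure imbalance. This stands, but none of them shows whether it does, and the SAP does not list the Charlson components. Likewise, the 22 of 33 is a share of codes, not of patients, so the documents do not support calling either flag mainly a marker of hypertension.

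Fourth, the outcome definition limits misclassification: a severe event needs a primary COPD diagnosis, so an episode coded primarily as heart failure does not count as one. This reduces the concern without removing confounding by true differences in risk.

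**Conclusion.** The point holds as a cheap improvement, not as a flaw that undermines the primary analysis. Heart failure is not isolated as a diagnosis in the score, the drug flag is non-specific, and the one specific term is limited, uncoded, missing from Table 1 and possibly a slip for COPD. The inconsistency between SAP 7.3 and both protocol 9.3.3 and Table 1 is documented and needs settling whichever item was meant.

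The size and direction of any bias cannot be derived from the documents. The shift of a null HR to about 0.96 to 0.985 rests on assumed post-matching imbalances of 8% vs 12% to 9% vs 15%, both beyond the plan's 0.1 threshold, and an assumed event hazard ratio of 1.5 to 2.0. With 9% vs 11% it is only 0.986 to 0.992. A reader might take these figures as an expected bias in favour of Tio/Olo. They are not: no passage gives heart failure prevalence by arm or says which treatment such patients tend to receive.

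**What to change.** 1. Reconcile the admission item in SAP 7.3 with protocol 9.3.3 and Table 1. Give whichever item is kept both diagnosis codes and a Table 1 row.
2. In Appendix 4, separate a heart failure/cardiomyopathy covariate from the remaining cardiovascular codes: ICD-9 425 and 428; ICD-10 I42, I43 and I50; plus the hypertensive heart disease subcodes within 402, 404, I11 and I13 that denote heart failure. The row's existing inpatient-or-repeated-outpatient rule can be kept. Enter the covariate in the propensity score and report it in Table 1 with its own ASD, so that the 0.1 rule applies to it.
3. Check why C03CA01, C03DA01 and C09DX04 are absent from the heart failure drug list, and correct the list or record the reason.

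Restricting C09AA and C09CA codes to patients who also have a heart failure diagnosis is not advised, because it would duplicate the new flag. Splitting the other cardiovascular groups is optional.

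Cost: no new data, one or two more binary covariates and a few table rows. There may be slightly fewer matches at the 0.06 SD caliper; the documents do not allow an estimate of how many.
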